3.3 Secondary Endpoints

3.3.1 Secondary Safety Endpoints

Local and systemic vaccine reactogenicity and/or allergy
Serious adverse events occurring during the 30 days following the additional dose of vaccine
Treated acute cell-mediated and/or antibody-mediated allograft rejection (clinical or biopsy-proven) within 60 days following the additional dose of vaccine
Development of de novo donor-specific anti-HLA antibody within 90 days of the vaccine
Graft loss within 60 days of the vaccine
Death within 60 days of the vaccine

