In a recent cohort of 741 organ transplant recipients who received two doses of either the Moderna or Pfizer-BioNTech vaccine, reactogenicity was similar to what has been reported in immunocompetent people: pain at injection site, fatigue, and headache were common. Severe reactogenicity (defined as preventing daily activity) occurred in 1-2% of study participants. Systemic reactogenicity was more common after the second dose of vaccine. There was an increased risk of local reactogenicity among recipients who

were maintained on an immunosuppressive regimen that included corticosteroids or mTOR inhibitors, and also among those who received the Moderna vaccine. There were no cases of anaphylaxis. There was one case of acute allograft rejection after the second dose of vaccine.³⁶

Infrequent cases of myocarditis or pericarditis have been reported after the use of COVID-19 vaccines containing the SARS-CoV-2 S-antigen. Myocarditis and pericarditis have been reported in greatest numbers in males under the age of 40 years following a second dose of mRNA vaccines, but cases have been reported in older males and in females as well, and also following other doses, and other vaccine platforms, including after doses of an adjuvanted protein vaccine. The observed risk is highest in males 12 to 17 years of age. While some cases required intensive care support, available data from short-term follow-up suggest that symptoms resolve in most individuals with conservative management. Information is not yet available about potential long-term sequelae. The risk in children younger than 12 years old is currently being assessed, and both the size of the database and length of follow-up in this population are relatively smaller than that of those older than 12 years old. Therefore, the characterization of the risk in children younger than 12 years old is not as well-known as in adolescents and adults.

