12.2.7 Serious Adverse Event (SAE)

An adverse event or suspected adverse reaction is considered “serious” if, in the view of either the investigator or Sponsor DAIT/NIAID, it results in any of the following outcomes (21 CFR 312.32(a)):

1. Death.
2. A life-threatening event: An AE or SAR is considered “life-threatening” if, in the view of either the investigator or Sponsor [DAIT/NIAID], its occurrence places the subject at immediate risk of death. It does not include an AE or SAR that, had it occurred in a more severe form, might have caused death.
3. Inpatient hospitalization or prolongation of existing hospitalization.
4. Persistent or significant incapacity or substantial disruption of the ability to conduct normal life functions.
5. Congenital anomaly or birth defect.
6. Important medical events that may not result in death, be life threatening, or require hospitalization may be considered serious when, based upon appropriate medical judgment, they may jeopardize the subject and may require medical or surgical intervention to prevent one of the outcomes listed above.

Elective hospitalizations or hospital admissions for the purpose of conduct of protocol mandated procedures are not to be reported as an SAE unless hospitalization is prolonged due to complications.

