12.3 Grading and Attribution of Adverse Events

12.3.1 Grading Criteria

The study site will grade the severity of adverse events experienced by the study subjects according to the criteria set forth in the National Cancer Institute’s Common Terminology Criteria for Adverse Events (CTCAE) Version 5.0. This document (referred to herein as the NCI-CTCAE manual) provides a common language to describe levels of severity, to analyze and interpret data, and to articulate the clinical significance of all adverse events. The NCI-CTCAE has been reviewed by the NIAID Medical Monitor and Protocol Chair and has been deemed appropriate for the subject population to be studied in this protocol.

Adverse events will be graded on a scale from 1 to 5 according to the following standards in the NCI-CTCAE manual:

Grade 1 = Mild; asymptomatic or mild symptoms; clinical or diagnostic observations only; intervention not indicated.

Grade 2 = Moderate; minimal, local or noninvasive intervention indicated; limiting age appropriate instrumental activities of daily living (ADL: Instrumental ADL refer to preparing meals, shopping for groceries or clothes, using the telephone, managing money, etc.)

Grade 3 = Severe or medically significant but not immediately life-threatening; hospitalization or prolongation of hospitalization indicated; disabling; limiting self-care activities of daily living (ADL: Self-care ADL refer to bathing, dressing and undressing, feeding self, using the toilet, taking medications, and not bedridden.)

Grade 4 = Life-threatening consequences; urgent intervention indicated.

Grade 5 = Death related to AE.

For grading an abnormal value or result of a clinical or laboratory evaluation (including, but not limited to, a radiograph, an ultrasound, an electrocardiogram etc.), a treatment-emergent adverse event is defined as an increase in grade from baseline or from the last post-baseline value that doesn't meet grading criteria. Changes in grade from screening to baseline will also be recorded as adverse events but are not treatment-emergent. If a specific event or result from a given clinical or laboratory evaluation is not included in the NCI-CTCAE manual, then an abnormal result would be considered an adverse event if changes in therapy or monitoring are implemented as a result of the event/result.

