13.2 Endpoints/Outcomes

The primary endpoint is the proportional increase in antibody titer U/mL (using the Roche Elecsys® anti-RBD assay) at 30 days after the study dose of vaccine. Negative or very low antibody responses (<10 U/mL) will be imputed to 10 U/mL, to reduce the influence of measurement error on the proportional increase calculation among individuals with very low titers. Secondary safety endpoints include: local and systemic vaccine reactogenicity and/or allergy; serious adverse events occurring during the 30 days following the additional COVID-19 vaccine dose; treated acute cell-mediated and/or antibody-mediated allograft rejection (clinical or biopsy-proven) within 60 days following the COVID-19 vaccine dose; development of de novo donor-specific anti-HLA antibody within 90 days of the vaccine; graft loss within 60 days of the vaccine; and death within 60 days of the vaccine. Secondary efficacy endpoints include: SARS-CoV-2 PCR positivity; symptomatic COVID-19; COVID-19 requiring hospitalization; and longitudinal changes in SARS-CoV-2 antibody response during the study.

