13.4.3 Analyses of Secondary and Other Endpoint(s)/Outcome(s)

All binary secondary endpoints will be analyzed using a Fisher exact test. Severe adverse events will be analyzed by calculating the incidence rate difference with a two-sided 95% confidence interval for immunoreduction vs no immunoreduction participants.

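### The only between-arm safety estimate with a confidence interval is written for severe adverse events with no time window, while the listed endpoint is serious adverse events within 30 days

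*Combined protocol and SAP*

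**What the plan says.** The endpoint is worded consistently. Section 3.3.1 lists "Serious adverse events occurring during the 30 days following the additional dose of vaccine", the synopsis carries the same item, and the statistical section repeats it in 13.2 as "serious adverse events occurring during the 30 days following the additional COVID-19 vaccine dose". None of the three lists severe adverse events as an endpoint.

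The analysis text in 13.4.3 has two sentences. The first is general: "All binary secondary endpoints will be analyzed using a Fisher exact test". The second is specific: "Severe adverse events will be analyzed by calculating the incidence rate difference with a two-sided 95% confidence interval", comparing reduction with no reduction. It gives no window and no grade threshold. Elsewhere, section 13 specifies rank-sum or Fisher tests, so this is the plan's only between-arm effect estimate with a confidence interval.

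The protocol separates the two terms. Section 12.2.7 makes an event serious through its outcome, for example "Inpatient hospitalization or prolongation of existing hospitalization". Section 12.3.1 attaches severe to a grade: "Grade 3 = Severe or medically significant but not immediately life-threatening; hospitalization or prolongation of hospitalization indicated". Nothing in section 13 equates or redefines them.

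**The concern.** Applied as written, 13.4.3 estimates a between-arm difference for a set of events that is not the listed endpoint. A Grade 3 event that meets none of the outcome criteria in 12.2.7 enters the estimate. Both arms are vaccinated, so severe reactogenicity is an obvious source of such events.

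The endpoint's 30-day window also disappears. That matters because the protocol collects non-serious events over different periods in the two arms.

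At stake is the prespecified safety contrast in a trial whose intervention carries an acknowledged risk of alloimmune injury (5.3). For uncommon serious events, an interval shows how large a difference remains compatible with the data. A non-significant Fisher p value does not.

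**Working it through.** The plan gives no adverse event rate or precision target, so there is no figure to reproduce. The check is a comparison of texts, followed by two illustrations.

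**1. Event class and window**

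| Place | Event class | Window |
|---|---|---|
| Synopsis, 3.3.1, 13.2 | Serious | 30 days after the dose |
| 13.4.3, estimate with interval | Severe | None stated |
| 13.4.3, Fisher test | Any binary secondary endpoint, so serious events as yes/no | That of the endpoint |

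The estimate differs from the endpoint in both class and window. It is also unclear whether severe means Grade 3 only, which is how 12.3.1 uses the word, or Grade 3 and above. Grade 3 only would leave out Grades 4 and 5.

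**2. Collection periods for non-serious events (12.4.1 with 6.7.1)**

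- Vaccine-alone arm: 30 days after the vaccine.
- Reduction arm: from the start of reduction (5 days before the vaccine), through its end (14 days after), plus 30 days: 5 + 14 + 30 = 49 days.
- Difference: 49 - 30 = 19 days. Ratio: 49/30 = 1.63.

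Without a common window, the direction of the distortion depends on the denominator, which 13.4.3 does not state.

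- *Participants as denominator.* The reduction arm has 19 more days in which an event can be counted.
- *Person-days as denominator.* Early vaccine reactions are divided by unequal time. Assume 4 per arm at 200 per arm (13.7). Vaccine alone: 4/(200 x 30) = 4/6,000 = 0.67 per 1,000 person-days. Reduction: 4/(200 x 49) = 4/9,800 = 0.41. Reduction looks better with no true difference.

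**3. Effect on precision (all counts assumed, 200 per arm)**

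The difference is p1 - p2, with a Wald interval of ±1.96 x sqrt[p1(1-p1)/200 + p2(1-p2)/200].

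| Events, reduction vs vaccine alone | Difference (points) | 95% CI |
|---|---|---|
| Serious only, 8 vs 4 | 2.0 | -1.3 to 5.3 |
| Plus 2 non-serious per arm, 10 vs 6 | 2.0 | -1.8 to 5.8 |
| Plus 4 non-serious per arm, 12 vs 8 | 2.0 | -2.3 to 6.3 |

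The additions of 2 and 4 are 1% and 2% of 200, a scale borrowed from the cohort figure in 5.2. If instead only 6 vs 3 of the serious events are also severe, the difference is 1.5 points (-1.4 to 4.4). Adding 20 non-serious events per arm (26 vs 23) keeps 1.5 points and widens the interval to (-4.9 to 7.9). That is 10% per arm, an upper illustration and not a forecast.

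Events added equally to both arms therefore leave the expected risk difference unchanged and cost precision.

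**The case against.** The strongest reply is that severe is a slip for serious. No severe-event endpoint exists, and the sentence sits under the analyses of secondary endpoints. That is probably right, but the text does not settle it. Section 2.3 includes reactogenicity among the safety objectives, so a deliberate severe-event comparison is not excluded either. Both readings call for the sentence to be clarified before anyone chooses between them with open-label data in view.

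A reader might infer four stronger things that the documents do not support.

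- *That serious events go unanalysed, or that a difference in them is hidden.* The Fisher test covers them as a binary endpoint, they are collected for about 6 months (12.4.1), and the DSMB receives a listing (12.7.2.1). What is missing is the prespecified estimate and interval.
- *That hospitalised events of lower grade would drop out in number.* The Grade 3 definition itself includes an indication for hospitalisation, so most admitted events should reach Grade 3. Exceptions are possible but probably few.
- *That the protocol supplies a rate for the inflation.* Section 5.2 reports "Severe reactogenicity (defined as preventing daily activity) occurred in 1-2% of study participants". This comes from a cited two-dose cohort with its own definition of severe, whereas CTCAE Grade 3 refers to self-care activities. It is not a forecast for this trial, and no serious-event rate is given to set it against.
- *That the added events must be balanced between arms.* The hypothesis in 2.1 is a stronger vaccine response under reduction, and 5.2 reports that local reactogenicity varied with the immunosuppressive regimen. If severe reactions differ by arm, the estimate itself moves, for reasons unrelated to serious harm.

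**Conclusion.** The mismatch is real and rests on the text alone: 13.4.3 names a different event class from the endpoint and omits its window. Taken literally, the estimate would include non-serious Grade 3 reactions and lose precision. Without a common window it would also compare about 49 days of collection with 30. Serious events would have a test but no prespecified effect estimate or interval.

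The size of the effect cannot be derived from the documents. Under the assumed counts the loss of precision is modest at 1% to 2% added events per arm and becomes large only at rates near 10%. The unequal windows depend on no assumed event rate, but they matter only if a severe-event analysis is run without a common window. This is worth correcting before analysis; it does not threaten the trial's conduct or its primary result.

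**What to change.** In 13.4.3, make the subject of the sentence serious adverse events occurring within 30 days of the study vaccine dose, and keep the incidence rate difference and its two-sided 95% interval. This matches the synopsis, 3.3.1 and 13.2. State the denominator (participants or person-time) in the same sentence.

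If a severe-event analysis is also wanted, list it separately as a further safety analysis, with a grade threshold (for example Grade 3 or higher) and the same window after the dose in both arms.

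The cost is a one-sentence edit, plus one table if the second analysis is kept. Data collection, sample size and conduct do not change.

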13.4.4 Analyses of Exploratory Objectives

To assess whether timing between vaccine doses is associated with differential antibody response to vaccination, we will calculate the median value of time from last pre-study vaccine dose to study dose, and then repeat the analysis of antibody response, stratified by the timing between doses (above vs below the median). To assess whether there is a difference in antibody levels among those receiving additional doses of Pfizer versus Moderna vaccination, we will repeat the analysis of antibody response, stratified by type of dose.

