2.6 Exploratory Objectives

To identify immunologic correlates of vaccine response.

To evaluate immune activation in response to the vaccine.

To assess whether timing between vaccine doses is associated with differential antibody response to vaccination.

To assess whether there is a difference in antibody levels among those receiving additional doses of Pfizer versus Moderna vaccination.

3. Study Design

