13.4.2 Primary Analysis of Primary Endpoint(s)/Outcome(s)

The primary endpoint is a continuous measurement. All individuals whose primary endpoint is measured will be included in the analysis population.

For the comparison of immunoreduction vs no immunoreduction, we will reject the null hypothesis if the two-sided rank-sum p value comparing the -fold increase between the two groups falls below 0.05.

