13.7 Sample Size Considerations

Comparison of the primary endpoint will use a two-sided ranksum test. There will be 400 patients, 200 per treatment group. Power calculations assume an α of 0.05. The power of the study will depend on the distribution of -fold changes in each group.

We ran simulations in which -fold changes are log-normally distributed, and computed power based on the ratio of -fold change between the two groups. For example, if the average -fold increase in one group is a twofold increase and in the other group, a threefold increase, the ratio of -fold change is $3/2$ or 1.5. (This does not mean that each individual in one group experienced a twofold increase; some individuals would experience a greater increase, and some a smaller increase.) In the simulation, with an N of 400, generally the study has 80% power to detect a difference of 20% (e.g. mean 2.5-fold increase in one group vs 3-fold increase in the other.)

14. Identification and Access to Source Data**14.1 Source Data**

Source documents and source data are the original documentation where subject information, visits consultations, examinations and other information are recorded. Documentation of source data is necessary for the reconstruction, evaluation and validation of clinical findings, observations, and other activities during a clinical trial.

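### The planned median-split analysis of dose timing gives no estimate or test of timing, and no test of whether the effect of immunosuppression reduction depends on timing

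*Combined protocol and SAP*

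**What the plan says.** Section 2.6 lists as an exploratory objective: "To assess whether timing between vaccine doses is associated with differential antibody response to vaccination". Section 13.4.4 gives the method in two steps. First, "we will calculate the median value of time from last pre-study vaccine dose to study dose". Second, the team will "repeat the analysis of antibody response, stratified by the timing between doses (above vs below the median".

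The analysis to be repeated has to be found elsewhere. Section 13.4.2 contains the only inferential antibody analysis in the plan, a comparison of immunosuppression reduction with no reduction: "we will reject the null hypothesis if the two-sided rank-sum p value comparing the -fold increase between the two groups falls below 0.05". Section 13.4.5 promises to look at how participant characteristics relate to antibody levels, but names no method.

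Section 13.7 sizes the trial for the arm comparison only. On the test it says "Comparison of the primary endpoint will use a two-sided ranksum test"; on enrolment it says "There will be 400 patients, 200 per treatment group"; and on the significance level it says "Power calculations assume an α of 0.05". Its conclusion is that "generally the study has 80% power to detect a difference of 20" per cent. It states no SD and gives no figure for the timing question. On the interval itself, inclusion criterion 7 (Section 4.2) sets a 60-day minimum and no maximum. Its distribution is not described.

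**The concern.** The objective and the method ask different questions. The objective asks whether response varies with the interval. The method asks, separately among shorter-interval and longer-interval participants, whether the arms differ. Participants with short intervals are never compared with those with long ones.

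The objective can also be read as asking whether the arm effect differs by timing. The method does not answer that either, because it includes no test of the difference between the two within-half effects. The likely misuse is to see one significant half and one non-significant half and report that timing matters.

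**Working it through.** **1. The plan's own power figure.** Inputs from Section 13.7: 200 per arm, two-sided α 0.05, 80% power, ratio of fold-increases 1.2. The effect on the ln scale is ln(1.2) = 0.182. With rank-sum efficiency 3/π = 0.955 for normal data, the effective n per arm is 200 × 0.955 = 191. The SD is not stated, so solve for it:

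SD = 0.182 / [(1.960 + 0.842) × √(2/191)] = 0.182 / 0.287 ≈ 0.64 (0.28 on log10).

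A simulated rank-sum test at SD 0.636 gave 79% power. The 80% is therefore attainable, but it cannot be verified without the SD.

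**2. Power within each half.** A median split leaves about 100 per arm, effectively 95.5. The standard error is 0.636 × √(2/95.5) = 0.092, and 0.182/0.092 = 1.98. Power is Φ(1.98 − 1.96) ≈ 51% (simulated: 50%).

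**3. Discordant halves when timing does nothing.** With the same arm effect in both halves, P(exactly one significant) = 2 × power × (1 − power) = 2 × 0.51 × 0.49 = 0.50 (simulated: 49%). This depends on the unstated SD:

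| SD of ln fold-increase | Power, whole trial | Power, each half | Exactly one half significant |
|---|---|---|---|
| 0.40 | 99% | 88% | 21% |
| 0.64 | 80% | 51% | 50% |
| 0.80 | 61% | 35% | 46% |
| 1.00 | 43% | 24% | 37% |

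**4. Does the planned output respond to timing?** A constant arm effect of 0.287 SD (0.182/0.636) was simulated with a normal interval and timing slopes of 0, 0.5 and 1.0 residual SD per SD of interval. The average within-half arm difference stayed at 0.28 to 0.29 in both halves throughout. Exactly one half was significant in 49%, 51% and 47% of runs. The output is essentially the same whether timing has no effect or a large one.

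**5. If the halves were compared directly instead.** The plan does not do this, but it is the obvious small repair. For an effect linear in the interval T, the information kept is the squared correlation of T with the indicator T > median. This equals D²/(4 Var T), where D is the difference between the upper-half and lower-half means.

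- Uniform: D = 1/2, Var = 1/12; keeps 0.75, loses 25%.
- Normal: D = 2√(2/π), Var = 1; keeps 2/π = 0.637, loses 36%.
- Exponential above a 60-day floor: D = 2 ln 2, Var = 1 in units of the mean excess; keeps (ln 2)² = 0.480, loses 52%.
- Lognormal, log-SD 0.5 (simulated): loses 48%. At log-SD 0.8 it loses 63%.
- Two equal modes 4 or 6 SD apart (simulated): loses 19% or 10%.

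In power terms, take a linear effect that a Pearson correlation detects with about 80% power at N = 400. A rank-sum comparison of the halves detects it with about 60% (normal), 66% (uniform) or 46% (exponential). These figures include the small cost of using ranks.

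**6. What an interaction test could detect.** At SD 0.636, if the arm effects in the two halves differ by ln(1.2), the standard error of that difference is 0.636 × √(4/95.5) = 0.130. Power is Φ(0.182/0.130 − 1.96) ≈ 29%.

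**The case against.** The strongest reply is that this is one exploratory objective on a covariate that was not randomised, with no error-control claim attached. Showing the arm comparison within strata is a common descriptive display if the objective concerns the arm effect, and Section 13.4.5 leaves room for further exploration. That is a good reason to rate the point low. It does not supply a method: Section 13.4.5 names none, and two within-stratum tests without an interaction estimate invite the misreading in step 3.

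A second reply is that the phrase in Section 13.4.4 for what is repeated is loose enough to include a comparison between the halves. No such comparison is specified anywhere, so this would have to be written in.

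A third reply concerns adjustment for baseline titre, and it stands. Titre may wane with time since the last dose, so baseline titre may lie on the path being studied. It is also the denominator of the fold-increase. As the schedules in Appendices 2 and 3 read, the Roche assay is not marked at Day 0. Section 8.2 accepts a prior result for eligibility with no upper age limit. The age of the baseline value could therefore itself track the interval. Section 13.2 also sets titres below 10 U/mL to 10, which limits the measured fold-increase in low responders. Baseline adjustment should be a second analysis, not the default.

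**Conclusion.** The point holds. Section 13.4.4 does not answer the Section 2.6 objective under either reading, because it produces no timing estimate or test and no timing-by-arm test. This follows from the text and needs no assumption about distributions.

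The discordance figure of about one half rests on the back-solved SD of 0.64, log-normal fold-increases, and an arm effect of the planned 20% that is equal in both halves. It falls to 21% at SD 0.40 and 37% at SD 1.00.

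A reader might infer that the median split discards at least a third of the timing information, so that 400 participants count as 255 or fewer. The documents do not support this. They give only the 60-day floor. A uniform interval loses 25% (400 × 0.75 = 300) and a clearly bimodal one loses less. The loss also depends on the scale: a lognormal interval analysed in log days is normal and loses 36%. All of these losses describe a direct comparison of halves that the plan does not make, so they are secondary.

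The primary comparison and the safety analyses are unaffected. This is an improvement worth making, not a threat to the trial.

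**What to change.** Replace the timing part of Section 13.4.4 with the following:

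- Regress log fold-increase on time from the last pre-study dose to the study dose as a continuous term (log days, or a 3-knot restricted cubic spline), with arm and vaccine era as covariates. Era matters because Sections 6.1 to 6.6 tie the study vaccine to the protocol version, and the interval may track it.
- Report the timing coefficient with its 95% CI. If a spline is used, report the fitted curve and a joint test.
- Add a timing-by-arm interaction term and report it as an estimate with a CI. Given step 6, a non-significant interaction should not be read as evidence that timing is irrelevant.
- Show results with and without log baseline titre, and state why.
- Keep the median split for display only.

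The comparison of the two vaccine brands in Section 13.4.4 has the same gap: it repeats the analysis by brand without comparing brands. The same edit can cover it.

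The cost is SAP wording and a little more analysis. No new data are needed, since the last-dose date is already required for inclusion criterion 7 and for the planned median.

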13.3 Measures to Minimize Bias

All participants will be randomized to receive immunoreduction or no immunoreduction prior to receipt of the vaccine. Randomization will be clustered by study site, and stratified by pre-dose titer (<50 vs ≥50 U/mL). Treatment group assignment will be unmasked to participants and clinical study staff. All laboratory staff will be masked to treatment assignment.

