13.4.5 Descriptive Analyses

Baseline and demographic characteristics will be compared between groups using a ranksum test for continuous variables and a Fisher exact test for binary/categorical variables. The relationship between demographic and other characteristics and antibody levels will be explored.

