13.6 Statistical Hypotheses

All analyses are superiority framework; the null hypotheses are that there is no difference in outcome rates between participants who do / do not receive immunoreduction. The alternative hypotheses for both safety and efficacy outcomes is that the outcome occurs more frequently in the immunoreduction group.

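### The exploratory Pfizer-versus-Moderna objective is addressed by repeating the immunosuppression-arm test within each product, which gives no between-product estimate or test

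*Combined protocol and SAP*

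**What the plan says.** The objective, in section 2.6, is a contrast between products: "To assess whether there is a difference in antibody levels among those receiving additional doses of Pfizer versus Moderna vaccination". Section 13.4.4 restates it and gives the method in one clause: "we will repeat the analysis of antibody response, stratified by type of dose".

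The analysis to be repeated is in section 13.4.2. Its contrast is "For the comparison of immunoreduction vs no immunoreduction", and its rule is "we will reject the null hypothesis if the two-sided rank-sum p value comparing the -fold increase between the two groups falls below 0.05". Section 13.6 states the hypotheses for the same factor only: "the null hypotheses are that there is no difference in outcome rates between participants who do / do not receive immunoreduction".

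On allocation, section 13.3 says "All participants will be randomized to receive immunoreduction or no immunoreduction prior to receipt of the vaccine", and Appendix 1 sends a randomised participant to one of two schedules, vaccine alone or reduction plus vaccine. Neither place describes an allocation to product.

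The nearest other text is in section 13.4.5: "The relationship between demographic and other characteristics and antibody levels will be explored". It does not name vaccine product, a test or a model.

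Section 13.4.4 handles the dose-timing objective in the same way. It splits participants at the median interval since their last pre-study dose and repeats the antibody analysis in each half.

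**The concern.** The stated analysis does not address the stated question. Stratifying an arm comparison by product asks whether immunosuppression reduction works among Pfizer recipients and whether it works among Moderna recipients. It does not say which product gave the higher titres, or by how much.

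Two things are at stake. First, a prespecified objective would have no prespecified answer, so any product comparison that is eventually reported would have its method chosen after the data were seen. The question is not idle: section 1.3 cites a cohort in which receipt of the Pfizer product was associated with lack of response. Second, two stratum p values invite the reader to treat one significant and one non-significant result as evidence of a product difference. That pattern tests neither a product difference nor a product-by-arm interaction.

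**Working it through.** **1. Question against method.**

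| | Factor compared | Source |
|---|---|---|
| Objective | Pfizer vs Moderna | 2.6, restated in 13.4.4 |
| Planned analysis | the antibody analysis, repeated by product | 13.4.4 |
| Antibody analysis as defined | reduction vs no reduction, two-sided rank-sum, 0.05 | 13.4.2 |
| Null hypotheses | reduction vs no reduction | 13.6 |

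The output is two arm comparisons. No row supplies a product contrast.

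**2. Why the within-product tests do not inform the objective.** Suppose one product multiplies every fold-increase by a constant. On the log scale this adds the same amount to everyone in that stratum. Ranks within the stratum do not move, so the within-stratum p value does not move. The floor at 10 U/mL in section 13.2 can create ties and disturb this slightly when an arm effect exists. With no arm effect the two arms are still exchangeable within a product, and the test rejects at its nominal level.

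**3. Simulation of that argument.** From section 13.7: N = 400, alpha 0.05, log-normal fold changes, and 80% power for a ratio of 1.2. The plan gives no SD, so the 80% cannot be checked outright. Solving for the SD of the natural-log fold change, with the rank-sum efficiency factor 3/π:

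SD = ln(1.2) × √(200 × 0.955 / 2) / (1.960 + 0.842) = 0.1823 × 9.772 / 2.802 = 0.636.

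Simulated power at SD 0.635 was 0.798, which reproduces the stated figure. SD 1.5 was run as a wide alternative. Assumptions: equal product split and no arm effect.

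| True product ratio | SD | Arm test within each product rejects | Direct product rank-sum rejects |
|---|---|---|---|
| 1.2 | 0.635 | 4.7%, 5.3% | 80% |
| 1.2 | 1.5 | 4.6%, 4.5% | 22% |
| 1.5 | 0.635 | 4.6%, 5.0% | 100% |
| 1.5 | 1.5 | 5.4%, 5.2% | 74% |
| 2.0 | 0.635 | 5.1%, 5.0% | 100% |
| 2.0 | 1.5 | 5.2%, 5.3% | 99.5% |

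A 70:30 split at ratio 1.5 and SD 0.635 gave 5.0% in each stratum and 100% for the direct test. The planned tests stay at about 5% throughout.

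**4. How often the two strata disagree when the products do not differ.** Let Z be the expected z statistic for the arm effect in all 400 participants. A stratum holding share s has expected z of Z√s and power p = Φ(Z√s − 1.96) + Φ(−Z√s − 1.96). The chance that exactly one stratum is significant is p₁(1 − p₂) + p₂(1 − p₁).

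| Overall power for the arm effect | Z | Split | p₁, p₂ | Exactly one significant |
|---|---|---|---|---|
| no arm effect | 0 | any | 0.05, 0.05 | 2 × 0.05 × 0.95 = 10% |
| 22% (ratio 1.2 at SD 1.5) | 1.19 | 50:50 | 0.134, 0.134 | 23% |
| 80% (section 13.7) | 2.80 | 50:50 | 0.51, 0.51 | 2 × 0.51 × 0.49 = 50% |
| 80% | 2.80 | 70:30 | 0.65, 0.34 | 0.65 × 0.66 + 0.34 × 0.35 = 55% |
| 99% | 4.29 | 50:50 | 0.86, 0.86 | 24% |

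The simulated stratum powers for the 80%, 50:50 row were 0.50 and 0.51, in agreement. The range of about 10% to 55% describes these scenarios and is not a bound. A more lopsided split can go higher: at 90:10 with 80% overall power, p₁ = 0.76 and p₂ = 0.14, giving 0.76 × 0.86 + 0.14 × 0.24 = 69% with these rounded powers.

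**The case against.** The best defence is that the clause is loosely worded. It does not cite 13.4.2, its phrase for the antibody analysis is never defined as a term, and the same sentence opens by naming a Pfizer–Moderna difference. The authors may have meant antibody results shown by product, side by side. That is possible, but no between-product test, estimate or model is written anywhere, and the only antibody-response test available to repeat compares the arms. Even on the generous reading, the method is missing.

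A second defence is that 13.4.5 already covers product under its general exploration of characteristics. Product could be included there, but the sentence commits to nothing that would answer the objective.

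Third, a reader might infer that product is plainly unrandomised. The documents are less tidy. Section 3.1 can be read as randomising to a vaccine of either brand with or without reduction, and sections 6.9 and 8.3.2 speak of an assigned vaccine. The supportable statement is that only immunoreduction is described as randomised (13.3, Appendix 1) and that no product allocation is described.

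Fourth, a reader might take the 50% row above as the size of the defect. It is one scenario, resting on an equal split and an arm effect tuned to 80% power. It also measures misuse of subgroup p values, not the missing contrast. The documents give neither a product split nor an SD, so only a range is defensible.

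Finally, this is one of four exploratory objectives, with no power claim attached. That stands, and it limits the weight of the point.

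**Conclusion.** The point holds in this form: as written, section 13.4.4 gives an arm effect within each product and no estimate or test of the product difference that section 2.6 asks about. This follows from the text and does not depend on any assumed SD or split. With no arm effect, the within-product tests reject at about 5% whatever the true product ratio. The 10% to 55% for discordant strata is secondary. It rests on assumed arm effects and on splits between 50:50 and 70:30.

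Two stronger readings are not supported. The trial is not unable to answer the question: the data needed for a direct comparison are collected, and only the stated analysis falls short. Nor does the gap reach the primary comparison or the safety analyses, which do not use product. The dose-timing objective has the same mismatch. The correction is worth making because it is cheap, but its importance is modest.

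**What to change.** Replace the product sentence in 13.4.4 with a direct comparison of Day-30 titre or fold-increase between Pfizer and Moderna recipients. It should account at least for arm, baseline titre and vaccine formulation or period, and for site where feasible. Formulation matters because the products moved from monovalent to bivalent to the 2023-2024 formula across protocol versions (6.1 to 6.6). Site matters because centres receive whatever is available to the study (6.5.1, 6.6.1).

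Either of two methods would do:
- a rank-sum test of product stratified by these factors, which keeps the plan's rank-based approach;
- a log-scale regression reporting a geometric mean ratio with 95% CI, with a check on the effect of values set to 10 U/mL.

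A longer list of covariates is not needed for an exploratory objective. If effect modification is of interest, report the product-by-arm interaction separately, and do not infer it from the stratum p values. State that no randomisation of product is described and that the comparison is therefore observational.

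Reword the dose-timing sentence likewise, so that antibody response is compared directly across intervals with arm accounted for.

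The cost is a few lines of SAP text and one additional analysis per objective on data already collected. No visits, samples or participants are added.
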